8 PROVISIONS FOR MONITORING STUDY PROGRESS	24
9 STATISTICAL CONSIDERATIONS	25
9.1 Study Hypotheses	25
9.2 Sample Size Considerations	26
9.3 Analysis Plan	27
10 QUALITY CONTROL AND QUALITY ASSURANCE	31

10.1	Training	31
10.2	Quality Monitoring	31
10.3	Data and Safety Monitoring Board	32
11	ETHICS/PROTECTION OF HUMAN SUBJECTS	33
11.1	Ethical Standards	33
11.2	Institutional Review Board.....	33
11.3	Informed Consent Process.....	33
11.4	Exclusion of Women, Minorities, and Children (Special Populations).....	33
11.5	Subject Confidentiality.....	34
12	COMMUNITY INVOLVEMENT PLAN.....	35
13	PUBLICATION/DATA SHARING POLICY	36

PROTOCOL SUMMARY

Title:

Evaluating the Role of Incision Height in Trichiasis Surgery Outcomes

Précis:

In this trial we will randomize 4,953 individuals with previously unoperated trichiasis on a 1:1:1 basis to bilamellar tarsal rotation trichiasis surgery with an incision height of 3mm, bilamellar tarsal rotation trichiasis surgery with an incision height of 5 mm, or Trabut surgery. Participants will receive trichiasis surgery and will be followed at 1 day, 2 weeks, 6 weeks, 12 months and 3 years after surgery. The primary outcome is development of post-operative trachomatous trichiasis (PTT) within 12-18 months after surgery. Logistic regression analyses will be performed to compare the rates of PTT in the 3 versus 5 mm incision BLTR groups, in the 3 mm BLTR versus Trabut group, and in the 5 mm BLTR versus Trabut group, adjusting for demographic characteristics and pre-operative trichiasis severity.

Objectives:

Primary objectives:

- 1) Examine whether the rate of post-operative trichiasis differs significantly for incisions placed 3 mm from the eyelid margin compared to incisions placed 5 mm from the eyelid margin.
- 2) Examine whether the rate of post-operative trichiasis differs significantly between surgery performed with the Trabut procedure versus bilamellar tarsal rotation with 3 mm incision height.
- 3) Examine whether the rate of post-operative trichiasis differs significantly between surgery performed with the Trabut procedure versus bilamellar tarsal rotation with 5 mm incision height.

[figure not shown]
Secondary objectives:

- 1) Determine whether the frequency of moderate/severe eyelid contour abnormalities differs following surgery performed with the bilamellar procedure when the target incision height is 3 mm versus 5 mm
- 2) Compare the frequency of moderate/severe eyelid contour abnormalities at one year between surgeries

performed with bilamellar 5 mm incision height and Trabut.

- 3) Compare the frequency of moderate/severe eyelid contour abnormalities at one year between surgeries performed with bilamellar 5 mm incision height and Trabut.

Population:	Participants will be recruited from the Hadiya Zone of the SNNPR Region in Ethiopia. All individuals with previously unoperated trichiasis in at least one eye, aged >18 years, and living in the area will be eligible to participate. We aim to enroll 1,500 individuals during the 2016/2017 surgical campaigns being supervised by Orbis International (we will recruit from January to April), an additional 2,500 individuals during the 2017/2018 campaign (October to April), and approximately 1,000 in the Fall/Winter 2018/2019 campaign.
Description of Intervention:	Trabut surgery involves a partial-thickness incision through the upper eyelid parallel to the eyelid margin. Bilamellar tarsal rotation involves a full-thickness incision through the upper eyelid. For bilamellar surgery, the height of the incision will be assigned at 3 mm or 5 mm from the eyelid margin. For Trabut, it will be assigned at 3 mm.
Study Duration:	6 years
Subject Participation Duration:	3 years
Estimated Time to Complete Enrollment:	Recruitment is scheduled for mid-January 2017 - April 2017 and mid-October 2017 through March 2018 to account for the rainy season.

STUDY DESIGN SCHEMATIC:

2 INTRODUCTION: BACKGROUND INFORMATION AND SCIENTIFIC RATIONALE

2.1 Background and Rationale

Trichiasis is an important cause of blindness in developing countries with limited access to water and sanitation measures. The disease primarily affects adult women, although in areas where trachoma is highly-endemic, trichiasis is occasionally diagnosed in young children. Surgery is available to correct trichiasis, but long-term success rates are suboptimal in many settings. Two primary surgical procedures are used, bilamellar tarsal rotation (BLTR; bilamellar) and posterior lamellar tarsal rotation (PLTR), also known as Trabut.

Surgical Procedure Comparison

A recent trial conducted in the Amhara region of Ethiopia compared BLTR and Trabut and found a significant reduction in post-operative trichiasis following Trabut as compared to BLTR (22% vs. 13%; Adjusted Odds Ratio 1.96; 95% CI: 1.40-2.75). The trial employed Trabut-trained surgeons who received conversion training to perform BLTR. Each surgeon performed both procedures as part of the trial. The trial was exceptionally well run, and some programs are now strictly training surgeons with Trabut. However, there is much debate over whether the trial results are broadly applicable for experienced surgeons who were first trained in BLTR and for newly trained surgeons. Specifically, since the release of the trial results, two meetings of the global trichiasis community have been held (one a WHO-sponsored meeting of trichiasis experts and the other the annual program review of the organization performing the largest volume of trichiasis surgeries worldwide, which included global experts from most trachoma-endemic countries). At both meetings, experts strongly recommended that another trial should be conducted which utilizes BLTR surgeons who receive conversion training to Trabut. Additionally, [name] is a member of the planned trials and has indicated strong in-country support for the need for an additional study to examine this question. In the planned trial, we will compare post-operative trichiasis rates for surgeries performed with each of these procedures. Surgeons will be either newly trained in both procedures or will be BLTR surgeons who have received conversion training in Trabut and have performed at least 100 Trabut surgeries.

Incision Height Comparison

In both the BLTR and Trabut procedures an incision is made in the eyelid, parallel to the eyelid margin, such that inturned eyelashes can be corrected to their normal position. Currently, the recommended height for making the incision is 3 mm above the eyelid margin. However, preliminary evidence from bilamellar surgery trials suggests that this height may not be the best height for achieving optimal outcomes. Data from both the PRET trial and the recent Trabut versus BLTR trial show reduced post-operative trichiasis among eyelids operated with the BLTR procedure with an incision scar height

of 5 mm at 1 year versus a lower incision scar height. Specifically, the PRET trial examined the role of a surgical clamp (the TT Clamp) in improving bilamellar trichiasis surgery outcomes. Use of the TT clamp improved eyelid contour abnormalities and granuloma formation, but it did not improve risk of trichiasis returning (post-operative trichiasis). Evaluation of incision height scars for a subset of this population suggests that incisions that are made closer to the eyelid margin are more likely to develop post-operative trichiasis than eyelids with an incision further away from the eyelid margin. When surgeons perform TT surgery with the clamp, they are guided on where to place the incision, and by design of the clamp, the height of the incision is limited; hence, it is possible that the TT clamp did not improve post-operative trichiasis rates because the incisions in the TT clamp arm were closer to the eyelid margin than eyelids operated with standard instrumentation (without a TT clamp). We have conducted a similar analysis of incision scar heights for the Amhara based BLTR vs. Trabut trial and found similar results for the BLTR surgeries in that study. Incision scar height and post-operative trichiasis were not correlated in Trabut surgeries; however, rates of post-operative trichiasis in the higher scar height BLTR surgeries were similar to rates in the Trabut arm.

One goal of the planned trial is to determine whether altering the incision height to 5 mm can improve surgical outcomes. We will compare target incision heights of 3 mm and 5 mm among BLTR surgeries. We selected this comparison since 2 studies have provided a suggestion that increasing the incision height in BLTR surgeries could positively affect post-operative trichiasis rates.

The follow up period for this trial is one year after surgery. Historical evidence suggests that the majority of post-operative trichiasis occurs within the first year after surgery, and that most recurrence that happens after one year is more related to disease severity than to the manner in which the procedure was performed.

2.2 Potential Risks and Benefits

Potential Risks

The risks associated with this study are minimal. Trichiasis surgery is a standard procedure commonly performed in many countries, and all subjects enrolled in this study would receive trichiasis surgery regardless of whether they participate in the clinical trial. Theoretically, increasing the incision height could result in an increased risk of eyelid contour abnormalities since a larger portion of the tarsus must be everted. Preliminary data suggest that higher incision heights are not associated with an increased risk of eyelid contour abnormalities. However, it is important to be aware of this possible risk.

Potential Benefits

Participants enrolled in this study will not benefit directly from this study. Most trichiasis surgery programs do not follow their patients after sutures are removed. In this study,

we will evaluate patients 6 weeks, 12 months and 3 years after surgery. Participants may view this as a benefit.

3 OBJECTIVES

3.1 Study Objectives

This study has three primary objectives:

- 1) Examine whether the rate of post-operative trichiasis differs significantly for incisions placed 3 mm from the eyelid margin compared to incisions place 5 mm from the eyelid margin.
- 2) Examine whether the rate of post-operative trichiasis differs significantly between surgery performed with the Trabut procedure versus bilamellar tarsal rotation with 3 mm incision height.
- 3) Examine whether the rate of post-operative trichiasis differs significantly between surgery performed with the Trabut procedure versus bilamellar tarsal rotation with 5 mm incision height.

Secondary objectives:

- 1) Determine whether the frequency of moderate/severe eyelid contour abnormalities differs following surgery performed with the bilamellar procedure when the target incision height is 3 mm versus 5 mm
- 2) Compare the frequency of moderate/severe eyelid contour abnormalities at one year between surgeries performed with bilamellar 5 mm incision height and Trabut.
- 3) Compare the frequency of moderate/severe eyelid contour abnormalities at one year between surgeries performed with bilamellar 5 mm incision height and Trabut.

3.2 Study Outcome Measures

Post-operative Trichiasis

We will evaluate post-operative trichiasis at 4 time points after surgery: 2 weeks, 6 weeks, 12 months and 3 years. Patient examiners standardized against [name] or [name] will perform the assessments. The assessment is made by looking at the eyelid with the eye in primary gaze. Any eyelashes touching the eye with the eye in primary gaze are considered to be trichiatic. Presence of post-operative trichiasis (primary outcome) is defined as 1+ trichiatic eyelashes or evidence of recent epilation. If an eyelid has trichiasis at 2 weeks but not at a later point, the eyelid will be considered not to have post-operative trichiasis.

Eyelid Contour Abnormalities

We will evaluate eyelid contour abnormalities at each post-operative visit. The examiner will grade the presence of abnormality using the definition provided below in the statistical considerations chapter. Both field and photographic grades will be utilized. The field grade will serve as the primary grade for the primary study analyses; secondary analyses will utilize the photograph grade. Examiners will be standardized at the start of the 6-week visits.

Pyogenic Granuloma

Pyogenic granulomas occasionally develop after trichiasis surgery, and it is thought that these are a response to a foreign body, such as suture material or a jagged incision edge. The patient examiners will evaluate presence of granulomas at 6 weeks, 12 months, and 3 years (with primary outcome being granuloma formation by the 12-18 month visit). All granulomas will be noted, regardless of size.

4 STUDY ENROLLMENT AND WITHDRAWAL

Study participants will be recruited from patients presenting for trichiasis surgery in the Hadiya Zone, in southern Ethiopia. We will not exclude subjects based on race or gender; however, participants must be aged 18 or older.

4.1 Subject Inclusion Criteria

In order to be eligible to participate in this study, an individual must meet all of the following criteria:

- Aged 18 or older
- At least one eyelid with previously unoperated upper eyelid trichiasis
- Willing to comply with all study procedures and be available for the duration of the study

4.2 Subject Exclusion Criteria

An individual who meets any of the following criteria will be excluded from participation in this study:

- Inability to provide independent, informed consent
- All eyes with previously unoperated trichiasis are phthisical

4.3 Strategies for Recruitment and Retention

Subjects will be recruited on the day that they present for trichiasis surgery. We will collaborate with an ongoing surgical program in the area (Orbis International) and will assist them with identifying patients with trichiasis. Advance screening will be conducted by the Orbis team. All individuals with trichiasis who would like to have surgery will be scheduled for surgery within 2-4 weeks after screening. On the day of surgery, they will be told about the study and anyone interested in learning more will meet with a consent specialist to hear a full description of the study and to complete the consent process if eligible and interested. All trichiasis patients will receive surgery free of charge, regardless of participation in the trial.

Subjects will not receive compensation for participation. Participant retention is maintained through contact with a local community health worker, who lives in the village with the participants and has a long-term relationship with them. The project director will call community health workers approximately 2 weeks before upcoming study visits to remind them that they need to contact the subjects living in their village to bring them for the follow up visit. Also, during the surgery day and at each follow up, patients will receive reminder cards stating the date and location of the next follow up

visit. This approach has been extremely successful in our previous trials, with retention rates of over 95% of eligible subjects.

4.4 Treatment Assignment Procedures

4.4.1 Randomization Procedures

Participants will be randomized at the participant level to one of three arms: 1) BLTR with target incision height of 3 mm 2) BLTR with target incision height of 5 mm and 3) Trabut with target incision height of 3 mm. Both eyes will be operated with the same surgical procedure and incision height if both eyes need surgery. Randomization assignments will be prepared in individual opaque envelopes with the patient ID number on both the outside of the envelope and on the internal papers indicating the arm assigned. The envelope will be opened during enrollment by the Program Manager. The surgeon and surgical assistant will both confirm the assigned surgical procedure and incision height at the start of the procedure. They will be required to indicate the assigned procedure and height on the surgical evaluation form and to measure and record the actual height of the incision made. Incision heights will be measured for patients in all three randomization arms.

The randomization assignments will be developed at UNC. Each week reported assigned surgical procedures and incision heights will be compared against the master table to ensure the assigned procedure and heights are consistently being reported for each participant. Details on monitoring are available in the quality assurance section.

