4.4.2 Masking Procedures

The study subject and the outcomes assessment team will be masked to treatment assignment. However, the surgeon will not be masked to the treatment assignment since s/he must know what procedure to perform and what height to make the incision at. In order to ensure the outcomes assessors remain masked, they will not be present at the surgical site, and they will not have access to data from the baseline and surgical visit.

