5.1 Study Procedural Intervention Description

Surgeons will receive the surgical procedure and incision height assignment just prior to surgery for that participant. Immediately before beginning surgery, the surgeon will confirm with the surgical assistant what the procedure is (BLTR or Trabut) and if BLTR, what the assigned target incision height is.

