6.2 Baseline Ocular Exam and Surgery (Day 0)

The baseline exam occurs immediately after enrollment and just prior to surgery (all happen on the same day). The goal of this exam is to characterize trichiasis severity and visual acuity prior to surgery. Baseline trichiasis severity is an important predictor of post-operative trichiasis; hence, these data will be included in all models evaluating the outcome.

After the ocular exam, the patient receives trichiasis surgery.

Required Data Collection:

- Baseline Ocular Exam Form
- Surgical Evaluation Form

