9.3 Analysis Plan

We will follow these general analysis principles:

- The primary analyses will be performed according to the participant's assigned intervention.
- All participants who complete randomization and have surgery performed will be included in analyses.
- All events following surgery will be counted.
- All analyses will be conducted at the eye level, using the generalized estimating equations approach to correct standard errors (to account for the correlation between two eyes of a subject).
- Unless otherwise indicated, three sets of analyses will be performed: 1) BLTR 3 mm versus BLTR 5 mm and 2) BLTR 3 mm versus Trabut 3 mm 3) BLTR 5 mm versus Trabut 3 mm.

Post-operative Trichiasis Analyses:

The primary analyses will be based on the dichotomous outcome: presence or absence of post-operative trichiasis at any time point within 12-18 months following surgery. Both unadjusted and adjusted analyses will be performed. Adjusted analyses will account for the severity of pre-operative trichiasis, with severity defined based on the table below.

Trichiasis Severity Classification	Description
Mild	1-4 Eyelashes touching globe, no epilation OR 1-10 Eyelashes epilated, no eyelashes touching globe

Moderate	5-9 Eyelashes touching globe, no epilation OR 1-4 Eyelashes touching globe and 1-10 eyelashes epilated
Severe	5-9 Eyelashes touching globe and 1-10 eyelashes epilated OR 10+ Eyelashes touching globe, regardless of epilation status OR 11-20 Eyelashes epilated, regardless of eyelashes touching globe OR Entire eyelid epilated

(Gower et al. 2013. *JAMA Ophthalmol.*;131(3):294-301.)

Multiple secondary analyses of post-operative trichiasis will be performed. We will compare the severity of post-operative trichiasis between groups, with severity defined using the table above. First, we will compare the primary groups utilizing severity at first observation (6 weeks or 12 months for the primary outcome). Then we will compare groups using severity at final observation. This will allow us to determine whether one group has a higher ‘surgical failure’ rate and whether recurrent trichiasis progression varies across interventions. We will conduct both unadjusted and adjusted analyses.

Eyelid Contour Abnormalities:

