Primary analyses of eyelid contour abnormalities will be based on a dichotomous variable: presence or absence of moderate/severe contour abnormality at the last study visit where the participant was seen between 6 weeks and 12-18 months, , or at last visit before repeat surgery using the photograph grade, which will be based on the definitions below. For the purposes of this analysis, mild will be combined with “no abnormality” and moderate and severe will be combined to form the “moderate/severe contour abnormality” group.

Abnormality	Definition
Mild	Vertical deviation from the natural contour, 1 mm in height (less than half the pupil height in daylight) and affecting 1/3 of horizontal eyelid length
Moderate	Vertical deviation from the natural contour 1–2 mm in height (about the pupil height in daylight) or affecting 1/3–2/3 of horizontal eyelid length
Severe	Vertical deviation from the natural contour 2 mm in height (more than the pupil height in daylight) or a defect >2/3 of the horizontal eyelid length

(Gower et al. 2012 *PLoS Negl Trop Dis* 6(6): e1713)

Secondary analyses will explore the relationship between incision height and the full range of eyelid contour abnormalities, which will require use of the photographic grade that will be graded centrally.

Targeted versus Actual Incision Height:

We will conduct an analysis to compare the assigned incision height against the actual incision height measured during surgery. If more than 10% of the heights vary by more than 0.5 mm, we will conduct secondary analyses for each of the above analyses to determine whether the results of the actual incision height analyses are similar to the per-protocol analyses. If differences exist, we will report these analyses separately, but will emphasize that the per-protocol analyses are the primary analyses.

New Versus Conversion Surgeons

Analyses will also be conducted stratifying based on surgeons' prior experience. Specifically, we will conduct all above analyses based on whether surgeons were trained on both bilamellar and Trabut simultaneously, or whether they first learned bilamellar and received additional training in Trabut at a later time.

1-day Surgical Corrections

Finally, we will conduct an analysis to determine whether there is a difference in the rate of 1-day surgical corrections by study arm.

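### Surgeon is not named as a randomisation stratum, covariate or clustering level in a trial of operations; adjusting for it costs little, gains a little precision, and matters more because matching to surgeons is undescribed

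*Combined protocol and SAP*

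**What the plan says.** The protocol summary states that "we will randomize 4,953 individuals with previously unoperated trichiasis on a 1:1:1 basis". Section 4.4.1 adds: "Participants will be randomized at the participant level to one of three arms". It says the assignments are developed at the coordinating university, and it mentions no stratification or blocking factor.

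On the analysis, 9.3 says "Adjusted analyses will account for the severity of pre-operative trichiasis". The summary lists demographic characteristics as well. The only correlation that 9.3 models is that between two eyes of the same participant. The one analysis that involves surgeons is a stratification by training history: "Specifically, we will conduct all above analyses based on whether surgeons were trained on both bilamellar and Trabut simultaneously", or learned Trabut later.

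On the order of events, 4.4.1 says "The envelope will be opened during enrollment by the Program Manager". Section 6.2 puts the baseline examination and then surgery after enrolment, on the same day; the table in Section 6 allows up to 14 days from enrolment to surgery. Section 5.1 says "Surgeons will receive the surgical procedure and incision height assignment just prior to surgery for that participant", and 4.4.2 confirms that "the surgeon will not be masked to the treatment assignment". No section says how or when a participant is matched to a surgeon.

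Section 5.3 requires incision-height deviations to be reported cumulatively for each surgeon, so the surgeon's identity should already be in the data.

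**The concern.** In a trial of operations, the operator is an obvious possible source of variation in outcome. Two separate things follow from leaving the surgeon out.

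The first is precision. If surgeons differ in their rates of post-operative trichiasis, that variation stays in the error term of every arm comparison.

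The second is comparability. Individual randomisation balances surgeons across arms only if the choice of surgeon does not depend on the arm. The Program Manager knows the arm from enrolment, and surgeons differ in their Trabut background (2.1). If some cases went to particular surgeons because of the arm, the procedure effect would be mixed with surgeon skill. Neither the severity covariate nor GEE by participant would remove that. The weekly checks in 4.4.1 and 5.3 compare assigned with reported procedure and height; none is described that compares the mix of surgeons across arms.

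**Working it through.** **Inputs from the documents.** 4,953 participants randomised 1:1:1; 15% control rate; 25% relative reduction, so 11.25% and a 3.75-point target; 40% bilateral; between-eye correlation 0.24; 5% loss; two-sided alpha 0.05 (all in 9.1, 9.2 or the summary).

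**Assumptions.** The documents give neither the number of surgeons (taken as 6-20) nor the variation between them (taken as a logit SD of 0.3-0.8).

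**The plan's own figure.** From 1,098 bilateral subjects per arm: 1,098 × 3 = 3,294; 3,294 × 2 / 1.4 = 4,706; 4,706 / 0.95 = 4,953. These steps reproduce. The 1,098 itself does not follow from the stated alpha 0.05 and 80% power, which give 1,272 eyes × 1.24 / 2 = 789. That is a separate matter and errs on the large side. It matters here only because base power is then above 80%.

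**Effective size.**
- Followed participants per arm: 4,953 / 3 × 0.95 = 1,568.
- Eyes per arm: 1,568 × 1.4 = 2,196.
- Design effect: (0.6 + 0.4 × 2 × 1.24) / 1.4 = 1.137.
- Effective eyes per arm: 2,196 / 1.137 = 1,931. Power for 15% against 11.25% is then 93.2% at alpha 0.05.

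**Precision.** The share of outcome variance lying between surgeons is f = var(p_j) / (0.15 × 0.85), and removing it multiplies the effective size by at most 1 / (1 − f).

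| Logit SD | f | 1/(1 − f) | Power, alpha 0.05 | Power, alpha 0.05/3 |
|---|---|---|---|---|
| none removed | – | 1 | 93.2% | 85.5% |
| 0.3 | 0.011 | 1.011 | 93.5% | 86.0% |
| 0.5 | 0.031 | 1.031 | 93.9% | 86.7% |
| 0.8 | 0.071 | 1.076 | 94.8% | 88.2% |

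The last column shows the result if alpha were split over the three comparisons; the plan does not say that it is.

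A simulation of a logistic model with surgeon indicators (6-12 surgeons, 600 trials per setting) gave ratios of squared mean z of 1.007 at SD 0.3 and 1.03 at SD 0.6. In participants, that is 4,953 × 0.007 = 35 to 4,953 × 0.03 = 149.

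**Chance imbalance.** With J equal surgeons, q = 1/J, and the SD of the between-arm difference in one surgeon's share is √(2q(1 − q)/1,651): 1.3 points for J = 6 and 0.8 for J = 20. The resulting contribution to the risk difference, √(2 var(p_j)/1,568), has an SD of 0.14 to 0.34 points against the 3.75-point target. It is already part of the ordinary binomial variance. In simulations with 6, 10 or 20 surgeons and no dependence on arm, the unadjusted test rejected a true null in 4.6-5.4% of trials.

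**What dependence on arm would do (illustration only).** Take two equal surgeon groups with risks of 10% and 20%, and no true difference between arms. The false risk difference is the shift in case share × (0.20 − 0.10).
- 5-point shift: 0.5 points, which is 0.5 / 3.75 = 13% of the target.
- 10-point shift: 15.5% against 14.5%, so 1.0 point (27% of the target) and RR 0.935. With SE = √(2 × 0.15 × 0.85 / 1,931) = 1.15 points, the chance of significance in that direction is about 14%, against 2.5% with no shift.
- 20-point shift: 16% against 14%, RR 0.875, about 41%.

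No figure in the documents supports any of these shifts.

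**The case against.** The strongest reply is that participant-level randomisation already protects the test, and that surgeon adjustment is a preference. Most of this stands. Surgeons are to be trained in both operations and certified (2.1, 5.2, 10.1), so surgeon is crossed with arm by design. Chance imbalance is trivial at this size. The surgeon factor that the rationale singles out, training history, has its own planned analysis.

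A reader might infer that surgeons are chosen after the arm is known. The documents do not support that: they are silent. Section 5.1 fits equally well with a surgeon matched beforehand, 6.1 allows a surgeon to screen the patient before consent, and detailed methods are left to a Manual of Procedures that is not among the documents reviewed.

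A reader might also expect a large precision gain. A gain of 8-9% (about 400 participants) needs a logit SD of 0.9. Around 15%, that puts the middle 80% of surgeons at roughly 5% to 36%, which is extreme for surgeons certified on one checklist. The 10% and 20% example above corresponds to an SD of only about 0.4: (logit 0.20 − logit 0.10) / 2 = (−1.386 + 2.197) / 2.

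Finally, if surgeons were chosen after allocation, surgeon is a post-randomisation variable, and conditioning on it could itself bias the estimate. This stands, and it shapes the fix.

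What the reply does not answer is that analysis by training history leaves differences between individual surgeons unadjusted, and that no check of surgeon mix by arm is described.

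**Conclusion.** The point holds in a limited form. Surgeon is not named as a stratum, covariate or clustering level, although its identity should already be recorded. Without steering, the planned test is valid. The cost is about 1-3% of effective sample size at a logit SD of 0.3-0.6; in power at alpha 0.05, it is about 0.3 points at SD 0.3 and 1.5 at SD 0.8. These sizes rest on assumed numbers of surgeons and assumed variation between them.

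The better reason to act is that the rule for matching participants to surgeons is not described and the arm is known to staff before surgery. Bias from matching is a possibility that the trial can examine with its own data. It is not a demonstrated flaw, and the drift figures show only what an assumed shift would do.

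**What to change.** In 9.3, add surgeon as a categorical covariate to the adjusted GEE model for the primary outcome, alongside pre-operative severity, and state in advance how surgeons with very few cases are pooled. Report the estimate with and without surgeon. Tabulate arm by surgeon, and state how participants were matched to surgeons.

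If any enrolment remains, amend 4.4.1 so that the operating surgeon is recorded before the envelope is opened. The timeline in 6.5 shows recruitment ending in March of Year 4 (2019), so this part is probably too late. It would also be a change of field procedure, not just of wording.

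The analysis changes need SAP wording only, with no extra participants or forms, provided surgeon identity is recorded as 5.3 implies. There are two downsides. The odds ratio becomes conditional on surgeon, so it is not on quite the same scale as the unadjusted one. And if surgeons were chosen after allocation, the adjusted result must be read together with the arm-by-surgeon table and cannot be treated as automatically the better estimate.
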